9.2.3 Exclusion Criteria

Not applicable.

9.2.4 Patient Enrolment

This DUS is a European, multi-centric retrospective cohort study. The study is based on the secondary use of data of GD1 patients treated with eliglustat that have been prospectively and consecutively enrolled in healthcare databases of four European countries (France, Germany, Denmark and Israel).

9.2.5 Patient Withdrawal and Replacement

Not applicable.

9.2.6 Patient Identification Numbers

Each patient will be identified by an identification (ID) variable defined as follows:

• Patient ID: The unique patient identifier in the study database. This identifier must be different from the unique identifier routinely used in the data source (e.g., the national number, or ID number in medical charts).

9.3 Variables

A more detailed description of the variables described in this section can be found in the statistical analysis plan (SAP) and country-specific analytical dataset specification (ADS) documents.

Variables in the study will be identified using ICD-10 and ATC codes, where applicable.

9.3.1 Exposure Assessment

The exposure of interest is the eliglustat use characterised by its dose and duration of use. Any GD1 patient with at least one prescription of eliglustat will be included in the exposure assessment.

During the exposure period, a patient taking eliglustat might be at risk for undesirable effect due to concomitant drug use (Appendix 1 in Section 14.1) with potentiation or inhibition of the therapeutic effects of eliglustat or potentiation or inhibition of therapeutic effects of concomitant drugs.

9.3.2 Outcomes of Interest

Outcomes of interest include concomitant medication use in terms of therapeutic class and duration. The CMI are strong and moderate CYP2D6 inhibitors, strong and moderate CYP3A inhibitors, strong CYP3A inducers, P-gp substrates and CYP2D6 substrates. Simultaneous use of strong or moderate CYP2D6 inhibitors with strong or moderate CYP3A inhibitors concomitantly with eliglustat will be explored, if feasible. Other outcomes will be the prescriber's specialty and the type of patient visit (e.g., hospital or in outpatient settings).

Concomitant medication use will be identified using ATC codes available in each database.

The duration of drug use will be defined with a continuous variable (number of days) and also with a categorical variable. The categorical variables will be defined as follows: 1. Total use of concomitant medication will be defined as any prescription whatever the duration; 2. Chronic use of concomitant medication will be defined as total duration of single or consecutive prescriptions of 15 days or over.

Where information is available, and subject to Ethics Committee approval, data on prescriber's specialty will be defined as the specialty of doctors prescribing concomitant medications to GD1 patients (e.g., GPs, haematologists, neurologists, etc.). These data will enable to define the number and profile of health professionals managing these patients. Data on the type of patient's visit is intended to capture whether prescriptions of concomitant drugs to GD1 patients are written in hospital or in outpatient settings.

9.3.3 Covariates

The only important covariates required are age and sex. Also, the death date of patients will be necessary to compute duration of drug use.

9.4 Data Sources

This DUS is planned to take place in France, Denmark, Germany and Israel. Data sources of these countries accepted to participate but not all research agreements have been signed yet. In each of these countries, there are effective, population-based databases which provide a large coverage of the country. Also, national death registers are in place in all of these countries to ascertain the vital status of patients. Passive follow-up can be accomplished in all data sources thanks to a unique personal ID number which can be used to link together the information from several population-based registries.

Data from these databases will be used to identify GD1 patients treated with eliglustat. These databases cover a total population of approximately 100 million inhabitants.

These data sources can provide detailed data on eliglustat prescription and duration of use, and also on concomitant therapies listed in Appendix 1 in Section 14.1, provided that these drugs are marketed in the country.

In all data sources, data on the prescriber's specialty of eliglustat is available. However, there may be variability in the availability of these data, depending on decision of local competent authorities. In any event, the data from all data sources can address all DUS objectives. The data recorded in these data sources are considered to be valid for the information included in this study by the data holders.

Databases have been selected in European countries where eliglustat is approved and have been launched. Israel is considered as a European country since several agreements are in place between EU and Israel, including EMA agreements.

France

In France, the launching/reimbursement of eliglustat is effective since 09 November 2016.

France has a high-quality national healthcare database which covers around 99% of the French population. This database is one of the most important healthcare databases in the world. Since 01 April 2017, the "Système National des Données de Santé" or national health data system (SNDS) gathers various health-related databases in France, including the social security database ("Système National d'Information Inter Régimes de l'Assurance Maladie" or national health insurance information system [SNIIRAM], main database set up in 2003) and the hospital records ("Programme de Médicalisation des Systèmes d'Information" or Medicalisation Programme of Information Systems [PMSI]). Since June 2018, the cause of death collected by the CépiDc ("Centre d'épidémiologie sur les causes médicales de décès" or epidemiological centre on medical cause of death) are progressively integrated to the SNDS. In the future, disability data and data from private health insurances will be available.

The French database contains outpatient data (i.e., expenses and reimbursements of medical visits and drugs, type and number of drugs delivered, date and nature of paramedical interventions, etc.) and hospitalisation data (i.e., admission date, duration of stay, main and associated diagnosis, medical acts, etc) through a unique personal identification number (NIR). All diagnoses are based on the ICD-10. Also, patient characteristics (i.e., sex, year of birth, place of residence and death data) and healthcare professional characteristics (i.e., speciality and type of practice) are available in the database. The main limitation of this database is the absence of data regarding clinical

information, biological results and risk factor, and few social data. Another limitation concerns hospitalised patients for whom no details on the drugs used during hospitalisation are available (except for some expensive drugs). Moreover, drug data available in this database concern drugs actually delivered to patients, which means that patients have actually taken the prescribed drugs from pharmacies. However, this does not guarantee that patients actually took their treatment, but this information is more accurate than when prescriptions only are considered.

This database is increasingly made accessible to researchers and to studies on drug safety and effectiveness in recent years. Of note, data for year N are usually fully available in year N + 1 (updated in summer each year). Regarding the cause of death data, a time-lag of two years is observed.

Access to the SNDS database is supervised by the Health Data Hub (HDH) which is in charge to transmit the applications to the CESREES ("Comité éthique et scientifique pour les recherches, les études et les évaluations dans le domaine de la santé" or Ethical and Scientific Committee for Research, Studies and Evaluations in the Health Field). The CESREES evaluates the methodology of the study and approves (or refuses) the project within one month. The final step consists in submitting the application to the CNIL ("Commission Nationale de l'Informatique et des Libertés" or National Commission on Informatics and Liberty), the governmental body in charge of personal data protection. The CNIL needs to give its green light for accessing and using the data. The CNIL has two to four months for approving (or refusing) the application.

Denmark

In Denmark, the launching/reimbursement of eliglustat is effective since April 2015.

In Denmark, there are two centres for patients with rare diseases: one in Copenhagen and one in Aarhus. Patients with GD are all followed in Copenhagen University Hospital, which allowed to establish a GD registry. This registry includes data recorded in Excel files (demographic data of patients) and also in electronic medical charts (REDCap system). Therefore, the creation of a unique database gathering both types of data will be needed.

In Denmark, eliglustat is prescribed by a paediatrician who takes care of all Danish GD patients. Patients have to go fill their eliglustat prescription in a hospital pharmacy. Therefore, both prescription and delivery dates are recorded in the GD registry. Also, this registry contains all data related to the management of GD patients including vital status. Of note, the completeness of information extracted from medical charts is not guaranteed, and information on the speciality of the prescriber of concomitant medications is not always available. Data on common over-the-counter medications such as Paracetamol, are not registered anywhere.

Even though the completeness of data is not guaranteed, it is not planned to use the National Prescription Registry (NPR) to complete data from the GD registry because the process of getting NPR applications approved is known to be very long. Moreover, the NPR application would be useless for a small number of patients (the expected number of patients treated with eliglustat in Denmark is ten).

The advantage of this registry is the absence of time-lag between the prescription/delivery of drugs and availability of these data in the registry since data are routinely collected in medical charts. Therefore, if the data extraction occurs in December 2022, all data recorded until this date will be available for the study. Also, patients in the GD registry have already consented to share their data for research purposes; thus, there is no need for a validation from an Ethics Committee. Furthermore, the small cell will not be an issue.

Germany

In Germany, the launching/reimbursement of eliglustat is effective since 15 April 2015.

Since 2004, the Leibniz Institute for Prevention Research and Epidemiology (BIPS) has been working on the establishment and maintenance of the project-based German Pharmacoepidemiological Research Database (GePaRD). This database contains claims data from four statutory health insurance providers and covers about 25 million insured German since 2004 which represents approximately 20% of the general population of Germany.

GePaRD includes demographic characteristics for each person (sex, birth year, nationality, etc.), information on drug prescriptions, outpatient and inpatient services and diagnoses starting with the year 2004. Hospital data include the period of hospitalisation with the entry date and exit date, the reasons for admission and discharge, and the diagnostic and therapeutic procedures. Claims of outpatient physician visits contain diagnoses, treatments, and procedures. Prescription data are limited to reimbursable drugs and include dates of prescription and delivery, the amount of drug prescribed, and details on the prescriber such as his/her specialty. All diagnoses (inpatient and outpatient) are based on the German Modification of the International Classification of Diseases, 10th revision (ICD-10-GM). A linkage to the central pharmaceutical reference database adds information on the prescribed drug such as the ATC code, the packaging size and the defined daily dose. One limitation of this database is that in-hospital medications are not included in GePaRD (except expensive medications).

This database is updated on an annual basis (i.e., at the end of each year) with anonymised and validated data. Of note, the entire process from data delivery to availability for studies can take up to two years.

Access to the database is granted only to BIPS employees within the framework of officially approved research projects. It is not permitted to give third parties access to the data. However, BIPS can be commissioned to carry out drug utilisation or drug safety studies that are requested by health authorities (e.g., EMA).

Israel

In Israel, the launching/reimbursement of eliglustat is effective since 12 January 2017.

Maccabi Healthcare Services is the second health provider in Israel which counts 2.5 million members (about 27% of the Israel population). It is a state mandated organisation with medical records fully computerised since 1993. Membership is accessible to everyone; it is free and independent of status of employment, occupation and location. This healthcare database gathers data going back 30 years on demographic characteristics, mortality and emigration, all physician diagnoses, medical visits records, hospitalisation, laboratory results, prescribed and dispensed medications, and other services delivered to patients (e.g., scans and images). Due to the high cost of eliglustat, all GD patients treated with this medication are fully compensated by the government.

Of note, there is no time-lag between the prescription/delivery of drugs and availability of these data in the database. Therefore, if the data extraction occurs in December 2022, all data recorded until this date will be available for the study.

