8.2 Secondary Objective

The secondary objective of the DUS is to describe the healthcare service pattern (i.e., prescriber's specialty and types of patient visit) for the prescriptions of concomitant medications in patients treated with eliglustat. The relevance of prescriber's specialty and types of patient visit is to inform whether prescriptions to GD1 patients are made in hospital or in outpatients services, and to inform on the number of health professionals taking care of these patients.

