9.5 Study Size

Gaucher Disease is a rare disease, therefore no restriction on the number of participants will be made. In other words, all patients with GD1 and taking eliglustat will be included in the analysis. This will allow to maximise the statistical power and to minimise the small cell/identifiability issue. Indeed, this problem may arise due to the small number of patients with GD1.

Knowing that the SNDS covers 99% of the French population, the Danish GD registry covers all the Danish population, the GePaRD database covers about 25 million of Germans and the Maccabi database covers approximately 2.5 million Israelis, the DUS will cover approximately 100 million people.

According to estimated number of patients taking eliglustat in each data source, the expected minimum number of participants in the DUS is 128 (87 in the SNDS, 10 in Danish GD registry, 11 in GePaRD and 20 in Maccabi database).

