9.9 Limitations of the Research Methods

Biases relative to missing data or non-reporting of prescribed drugs should be minimal since registered data are mandatory for the payment or reimbursement of drugs by social security offices.

Nonetheless, the prescription databases involved in this study have the known limitation of the administrative data provided by health services and health professionals for reimbursement purposes or because of legal obligation. The type of collected data and the logic of data collection have not been primarily devised for being used for scientific purposes. Moreover, the protection of data privacy and confidentiality of medical records imposes strict boundaries on the type of data that can be registered in prescription databases. Hence, for a number of activities recorded in the database, the result of that activity is not recorded. However, in the light of the specific objectives of this study, this limitation should not impact the results.

There are no confounders and other sources of bias that could impact the DUS results. However, underreporting of information and misclassification of the study variables can occur due to missing information in the data. Selection bias is less likely to occur since all included data sources are nationally representative. The results of the study will be interpreted in context of the limitations.

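### Section 9.4 says every source can address every objective, but its own source descriptions show gaps in concomitant-drug capture in France, Germany and Denmark, and Section 9.9 calls non-reporting bias minimal

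*Protocol*

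**What the plan says.** Section 8.2 sets the secondary objective: to describe prescriber specialty and visit type for CMI, in part "to inform whether prescriptions to GD1 patients are made in hospital or in outpatients services". Section 9.1.2 ties visit type to the delivered drug and gives hospital as an example category. Section 9.7.4.2 counts patients by the type of visit during which a CMI delivery took place, again with hospital as an example.

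Section 9.4 concludes for all four sources: "In any event, the data from all data sources can address all DUS objectives". The country descriptions that follow it say:

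- **France (SNDS):** a limitation concerns "hospitalised patients for whom no details on the drugs used during hospitalisation are available (except for some expensive drugs").
- **Germany (GePaRD):** "in-hospital medications are not included in GePaRD (except expensive medications").
- **Denmark (GD registry):** "the completeness of information extracted from medical charts is not guaranteed". The specialty of the CMI prescriber is sometimes missing, and linkage to the national prescription registry is ruled out.
- **Israel (Maccabi):** no capture limit for CMI is stated.

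Section 9.9 states: "Biases relative to missing data or non-reporting of prescribed drugs should be minimal". The reason given is that registration is required for payment or reimbursement. The same section later concedes, in general terms, that underreporting and misclassification can occur.

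**The concern.** The general sentence in Section 9.4 credits the sources with a property that their own descriptions deny. The reason given in Section 9.9 does not repair this. Mandatory registration for payment says nothing about drugs given during a French or German hospital stay, which those databases do not itemise. It also does not apply to the Danish source, which is built from spreadsheets and medical charts at one hospital.

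Three results are exposed:

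1. **Visit type (secondary).** If the Section 9.7.4.2 count is applied as written, CMI given during French and German stays are missing from the in-hospital category, and a low or empty cell could be read as a finding.
2. **CMI proportions and durations (primary).** A patient whose only CMI exposure was as an inpatient is counted as a non-user, and inpatient days of use are not added to duration. Danish CMI missing from the charts has the same effect.
3. **Comparison between countries.** Section 9.7.1 says that analysis by source will allow prescribing patterns to be compared across countries. With unequal capture, part of any difference is an artefact.

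The direction matters because Sections 7.3 and 8 use the study to judge whether risk minimisation measures succeed in avoiding interactions. Missed CMI makes those measures look better than they are.

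**Working it through.** **Reproducing the plan's figure.** Section 9.5 expects "87 in the SNDS, 10 in Danish GD registry, 11 in GePaRD and 20 in Maccabi database", and says "the expected minimum number of participants in the DUS is 128". The sum is 87 + 10 + 11 + 20 = 128, which agrees.

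**Patients by stated capture limit for CMI (Section 9.4)**

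| Source | Stated limit | Expected n | Share of 128 |
|---|---|---|---|
| SNDS + GePaRD | no routine in-hospital drug data | 87 + 11 = 98 | 76.6% |
| Danish GD registry | chart completeness not assured; CMI prescriber specialty sometimes missing | 10 | 7.8% |
| Maccabi | none stated | 20 | 15.6% |

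The 76.6% is the share of patients in sources with the gap. It is not the share with a missed drug.

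**What the gap could do.** The documents give no figure for inpatient-only CMI use, so the inputs below are assumptions that show the shape of the bias. They are not estimates.

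*(a) CMI proportion.* Let p be the true proportion of users and h the share of users exposed only as inpatients. The observed proportion is p(1 − h). For p, take the pilot's 10/48 = 20.8% for CYP inhibitors (Appendix 3). That figure came from outpatient and day-hospital records, so it serves only as a convenient level.

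- h = 5%: 20.8% × 0.95 = 19.8%; users missed among 98 = 98 × 0.2083 × 0.05 ≈ 1.
- h = 30%: 20.8% × 0.70 = 14.6%; users missed = 98 × 0.2083 × 0.30 ≈ 6.

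*(b) Hospital share of CMI prescriptions.* Let H be the true share and u the fraction of hospital prescriptions that go to inpatients and so are unseen. The observed share is H(1 − u)/(1 − Hu). With H = 30%:

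| u | Calculation | Observed share |
|---|---|---|
| 25% | 0.225/0.925 | 24.3% |
| 50% | 0.150/0.850 | 17.6% |
| 75% | 0.075/0.775 | 9.7% |
| 100% | 0/0.700 | 0% |

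For any u above zero the observed share is too low. It reaches zero only if every hospital prescription is unseen.

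**Which definition of visit type applies.** Sections 8.2 and 9.3.2 speak of where a prescription is made or written. Sections 9.1.2 and 9.7.4.2 speak of deliveries and the visit at which they occur. Under the first definition, a hospital doctor's prescription dispensed in the community counts as hospital and may be visible. Under the second, the unseen deliveries are those made during stays. The hospital category is incomplete under both, and more so under the second.

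**The case against.** The strongest reply is that the gaps are disclosed and the objective can still be answered in part. Section 9.3.2 defines visit type by where the prescription is written. SNDS holds the prescriber's specialty and type of practice, and GePaRD holds prescriber details including specialty, so hospital-written prescriptions dispensed outside may be classifiable. The Abstract collects specialty and visit type only where feasible, and Section 9.7.4.2 lets visit types depend on the source. Section 9.4 itself calls the in-hospital gap a limitation, Section 9.9 admits that underreporting can occur, and detailed derivations are left to the SAP and country-specific dataset specifications.

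Much of this stands, and it limits the point. A reader might infer that the hospital-versus-outpatient question cannot be answered at all in France and Germany, or that the hospital cell there must be zero. The documents support neither, given the prescriber data and the exception for (some) expensive drugs. Nor do they show that classification by prescriber setting works in either source; for GePaRD only specialty is named.

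A reader might also want inpatient days taken out of CMI person-time, or pooled results given with and without Denmark. Neither quantity is planned. Section 9.7.3.3 uses patient proportions and summed delivery durations, and Sections 9.6 and 9.7.1 keep the sources separate.

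The reply does not rescue the two general statements. Disclosure under each country is what contradicts the unqualified sentence in Section 9.4. The concession in Section 9.9 names neither the in-hospital gap nor the Danish one, gives no direction, and follows a sentence that denies other sources of bias.

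**Conclusion.** The point holds as a contradiction within the protocol that affects how results will be read. Sources with 98 of 128 expected patients (76.6%) lack routine in-hospital drug data, and a further 10 (7.8%) depend on charts whose completeness is not assured. The in-hospital visit category is incompletely captured and biased downward in France and Germany. CMI proportions and durations can be understated in France, Germany and Denmark, and comparison between countries is affected by unequal capture.

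The direction follows from the stated limits alone. The size cannot be estimated, because the documents do not say how much CMI use occurs only during hospital stays or how much is missing from the Danish charts. The ranges of 1 to 6 missed users and of 24.3% down to 0% for the hospital share rest on assumed inputs. It would be wrong to read 76.6% as the proportion of patients with missed CMI.

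**What to change.** 1. **Section 9.4:** replace the general sentence with a statement, by source and objective, of what each database can and cannot address. Include the Danish gap in CMI prescriber specialty.
2. **Section 9.7.4.2:** in SNDS and GePaRD, limit the visit-type result to CMI dispensed outside hospital stays, classified by prescriber setting where that is available. Show drugs given during stays as *not observable*, never as 0.
3. **Denmark:** report CMI as chart-recorded minimum values, and caveat or omit them in the between-country comparison in Section 9.7.1.
4. **Section 9.9:** replace the statement that bias is minimal with the named in-hospital and Danish gaps and their downward direction. Drop the payment argument where it does not apply.

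This costs protocol wording, table labels and footnotes. It needs no new data. The downside is a narrower secondary claim.

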7.3 Risk Management Measures

The safety concerns relevant for eliglustat are primarily managed through routine risk minimisation activities: labelling recommendations and prescription status of the product, to be initiated and supervised by a physician knowledgeable in the management of GD.

Moreover, the following educational materials have been developed to reinforce knowledge and adherence of the prescribers and patients to the risks associated with the use of eliglustat, including:

- A guide for prescriber: targeted to specialists initiating and supervising eliglustat treatment including a checklist of steps to be performed prior to initiation of eliglustat.
- A patient alert card: targeted to Health Care Providers (HCP) who do not prescribe eliglustat regarding important drug-drug interactions with eliglustat and to ensure that the patient's risk for drug-drug interactions reach the relevant HCP. It is also targeted to patients who will be educated regarding self-medication, and to present the card to all other HCP at each visit.

Also, recommendations and precautions to be followed by healthcare professionals and patients for the safe and effective use of eliglustat have also been included in the summary of product characteristics and in the package leaflet of eliglustat.

This DUS will allow to assess the effectiveness of risk minimisation measures that have been put in place and also to improve them.

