8 RESEARCH QUESTION AND OBJECTIVES

As part of pharmacovigilance activities of eliglustat risk management plan, this DUS will allow to assess the effectiveness of risk minimisation measures (EU labelling, guide for prescribers and patient alert card) regarding understanding and implementing avoidance of significant drug-drug interactions.

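### The study is said to assess the alert card, which also targets self-medication, but the protocol's own source descriptions leave out non-prescription, non-reimbursed and in-hospital use, and section 9.9 does not say so

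*Protocol*

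**What the plan says.** **Purpose.** Protocol section 8 states what is to be evaluated: "effectiveness of risk minimisation measures (EU labelling, guide for prescribers and patient alert card) regarding understanding and implementing avoidance of significant drug-drug interactions". Section 7.3 repeats the claim and describes the card's two audiences. The first: "A patient alert card: targeted to Health Care Providers (HCP) who do not prescribe eliglustat regarding important drug-drug interactions with eliglustat". The second is the patient: "It is also targeted to patients who will be educated regarding self-medication".

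**Data.** Section 9.4 says the sources can supply the Appendix 1 drugs as long as these are marketed in the country, and that all sources can address all objectives. The country descriptions in the same section add limits:

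- Denmark: "Data on common over-the-counter medications such as Paracetamol, are not registered anywhere". The data come from a disease registry and medical charts of unguaranteed completeness, and the national prescription registry will not be used to fill gaps.
- Germany: "Prescription data are limited to reimbursable drugs". In-hospital drugs are absent apart from expensive ones.
- France: outpatient data rest on reimbursements and deliveries. In-hospital drugs are absent apart from some expensive ones.
- Israel: prescribed and dispensed drugs are held, and no limit is stated.

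**Limitations.** Section 9.9 opens: "Biases relative to missing data or non-reporting of prescribed drugs should be minimal". The reason it gives is that recording is compulsory for reimbursement. It later denies that confounders or other sources of bias could affect the results, then concedes in general terms that underreporting and misclassification can occur.

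**The concern.** The protocol ties its conclusion to a measure that works partly through self-medication, while two of its four sources are described as not holding the drugs a patient would obtain without a prescription or without reimbursement. The limitations section should be where this is reconciled, and it is not.

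Two readings of the results are at stake. Low recorded CMI use could be taken as successful avoidance of interactions, although one route to those interactions is not observed. And section 9.7.1 says that analysing the sources separately will allow prescribing patterns to be compared between countries. If the sources capture different fractions of use, part of any difference between countries comes from capture.

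**Working it through.** **1. The plan's own count.** Section 9.5 expects 87 patients in France, 10 in Denmark, 11 in Germany and 20 in Israel: 87 + 10 + 11 + 20 = 128, which agrees with the stated minimum.

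**2. How many patients sit in a source with a stated gap.**

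| Gap | Sources | Expected patients |
|---|---|---|
| Over-the-counter (Denmark) or non-reimbursable (Germany), explicit | Denmark, Germany | 10 + 11 = 21; 21/128 = 16.4% |
| In-hospital drugs, explicit | France, Germany | 87 + 11 = 98; 98/128 = 76.6% |
| At least one of these gaps | France, Denmark, Germany | 87 + 10 + 11 = 108; 108/128 = 84.4% |
| No limit stated | Israel | 20/128 = 15.6% |

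These are patients in affected sources, not patients whose CMI use is missed. A limit on non-reimbursed drugs in France can be inferred from the reimbursement basis of the data, but the protocol does not state it.

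**3. Does the section 9.9 argument cover the gaps?** Its premise is that drugs must be recorded to be paid for. That supports completeness for reimbursed outpatient drugs in a claims database. It does not reach over-the-counter drugs, non-reimbursable drugs, or the in-hospital drugs that section 9.4 says are absent. Nor does it describe Denmark, where the record is a medical chart, so there it fails even for prescribed drugs.

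**4. Possible size, under assumptions.** The documents give no capture sensitivity (Se). The only CMI-type proportion in the protocol is the pilot's 10/48 = 20.8% (Appendix 3). It covers inhibitors only, in patients not on eliglustat, and is used here purely as a base. With no false positives, observed = Se × true, so true = observed / Se:

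| Assumed Se | True use if 20.8% is observed | Observed use if 20.8% is true |
|---|---|---|
| 1.0 | 20.8% | 20.8% |
| 0.9 | 23.1% | 18.8% |
| 0.8 | 26.0% | 16.7% |
| 0.7 | 29.8% | 14.6% |
| 0.5 | 41.7% | 10.4% |

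Two countries with the same true use of 20.8%, one at Se 1.0 and one at Se 0.7, would show 20.8% and 14.6%: about 6 percentage points from capture alone.

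**5. Is the recorded proportion a lower bound?** Section 9.4 says for France that delivery does not guarantee intake. With specificity Sp, observed = Se × p + (1 − Sp) × (1 − p). Take p = 10/48 and Se = 0.8:

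- Sp 1.00: 16.7%
- Sp 0.95: 0.8 × 0.2083 + 0.05 × 0.7917 = 20.6%
- Sp 0.90: 0.8 × 0.2083 + 0.10 × 0.7917 = 24.6%

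Observed exceeds true once 1 − Sp > (1 − Se) × p / (1 − p) = 0.2 × 0.2083 / 0.7917 = 5.3%. Under-capture pushes the proportion down, but the net direction is not guaranteed.

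**The case against.** Several points on the other side are sound and limit the claim.

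- **Section 9.9 is narrower than it may look.** A reader might infer that it calls all bias from missing drugs minimal. It says this of prescribed drugs only, concedes underreporting in general terms, and says results will be read in light of the limitations. That stands. But the caveat names neither the missing drugs nor a direction, and it follows a flat denial of other bias.
- **The Danish example is not a CMI.** Paracetamol is not in the Appendix 1 lists, and nothing in the protocol says which listed drugs are sold without prescription, or are not reimbursed, in any of the four countries. A reader might infer a known loss of CMI use; the documents do not show its extent.
- **Non-capture is not uniform.** Over-the-counter or reimbursement limits are explicit for Denmark and Germany only. Section 9.1.1 also allows a CMI to be identified from a mention in the chart, so Danish capture is uncertain rather than nil.
- **The proportions are not strict lower bounds.** This is the tempting stronger reading, and step 5 of the working shows why it fails: recorded deliveries may not be taken.
- **The study is descriptive and much of its aim is measurable.** Section 9.1 says there are no comparative elements, there is no success threshold, and the secondary objective concerns prescriptions. The card's first audience, other health care providers, can be studied through recorded prescriptions. This confines the problem to the self-medication aim and to the wording of the conclusion, but sections 7.3 and 8 make no such distinction.

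**Conclusion.** The point holds as an inconsistency within the protocol. The blanket statement in section 9.4 that all sources serve all objectives, and the denial of other bias in section 9.9, do not fit the source descriptions in section 9.4. The self-medication aim of the alert card cannot be assessed for common over-the-counter drugs in Denmark or for non-reimbursable drugs in Germany, and no other source is described as covering it.

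Explicit gaps of that kind concern sources expected to hold 21 of 128 patients (16.4%). The in-hospital gap concerns sources holding 98 of 128 (76.6%). The amount of CMI use lost is not in the documents; the sensitivities and specificities in the working are assumptions and give no corrected estimate. What can be said is that non-prescription, non-reimbursed and in-hospital CMI use is likely under-captured, to a degree that differs by source. The correction is worth making because it changes what the study may conclude about risk minimisation.

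**What to change.** - **Sections 7.3 and 8:** limit the risk-minimisation conclusion to recorded prescriptions or deliveries, and state that the self-medication aim of the alert card is not assessed.
- **Section 9.4:** qualify the statement that all sources can address all objectives so that it agrees with the country descriptions.
- **Section 9.9:** confine the reimbursement argument to the sources it fits, and replace the sentence denying other bias. Say instead that non-prescription, non-reimbursed and in-hospital CMI use is likely under-captured to a degree that differs by source, so that differences between countries (section 9.7.1) may reflect capture rather than prescribing. Do not describe the proportions as strict lower bounds.

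The cost is a few sentences, with no new data or analysis. The downside is a narrower claim on risk minimisation.

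Flagging by country the Appendix 1 drugs obtainable without a reimbursed prescription would be optional detail for the statistical analysis plan or the country dataset specifications. Repeating table rows with and without such drugs is not needed. With 10 or 11 patients in a source, it could let small cells be derived by subtraction, which section 10.4 seeks to prevent where local rules require it.
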